*To assess the robustness of the primary MMRM results to the possible violation of the missing-at-random assumption, a sensitivity analysis using a pattern-mixture model based on non-future dependent missing value restrictions (Kenward et al, 2003) will be performed. The pattern for the pattern-mixture model will be defined by the patient's last visit with observed value. The observed MADRS total score at a visit is assumed to have a linear relationship with the patient's prior measurements. The missing values will be imputed under the assumption that the distribution of the missing observations differs from the observed only by a shift parameter value  $\Delta$ . The dataset with missing values will be analyzed using the same model as the primary analysis for between-treatment group comparisons at the end of the treatment. The imputation of missing values and the analysis will be performed multiple times and the inference of this sensitivity analysis will be based on the combined estimates using the standard multiple imputation technique. The values of  $\Delta$  will be selected as 0 to 8.*

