To assess the robustness of the primary MMRM results to the possible violation of the missing-at-random assumption, a sensitivity analysis using a pattern-mixture model based on non-future dependent missing value restrictions (Kenward et al, 2003) will be performed. The pattern for the pattern-mixture model will be defined by the patient's last visit with observed value. The observed MADRS total score at a visit is assumed to have a linear relationship with the patient's prior measurements. The missing values will be imputed under the assumption that the distribution of the missing observations differs from the observed only by a shift parameter value Δ . The dataset with missing values will be analyzed using the same model as the primary analysis for between-treatment group comparisons. The imputation of missing values and the analysis will be performed multiple times and the inference of this sensitivity analysis will be based on the combined estimates using the standard multiple imputation technique. The values for Δ will be selected as 0 to 8.

[figure not shown]

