12.0 DETERMINATION OF SAMPLE SIZE

The originally proposed primary efficacy variable is the change from baseline (ie., Day 7) at Day 8 in MADRS total score and the primary analysis population included the subset of patients who were placebo non-responders during the placebo lead-in period before randomization. Based on that the study was planned to randomize 700 patients (including both placebo responders and placebo non-responders), assuming standard deviation (SD) of 10 points, which provides 99% power to detect a difference of 3.25 points in MADRS total score between rapastinel 450 mg and placebo at a 2-sided significance level of 0.05.

While the study was ongoing, the primary efficacy variable was revised to be the change from baseline in MADRS score at the last visit, Day 21, and the primary efficacy study population was revised to include all randomized patients (placebo responders and placebo non-responders) based on the feedback by the FDA, EMA, and PDMA. Both of these changes were included in Amendment 2 of the protocol. At the same time of Amendment 2, a blinded data review was conducted for Studies RAP-MD-01, RAP-MD-02, and RAP-MD-03. The pooled SD for the three studies were 7.4, 8.0, and 8.7, respectively, all smaller than the originally assumed 10 points. Sample size was re-calculated using 8.7 as the common SD. The calculation used MMRM model with simulations; it also assumed correlation of 0.5 between the repeated measures and a common drop-out rate of 10% during the randomized treatment period and an additional 5% drop-out rate during the placebo lead-in period for all treatment groups. To have 90% power, the total sample size required is 360 patients. However, the study had already enrolled more than 390 patients with less than 5% of overall drop-out rate, surpassing the re-estimated sample size of 360 patients. The study enrollment was halted as soon as operationally feasible. The final sample size is approximately 420 patients (210 patients per treatment group).

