Note that the two distributions only differ from a shift (Δ) parameter. When $\Delta = 0$, the missing value y_s in Pattern $s-1$ is imputed based on the distribution of all observed data up to Visit s , as a result, leading to missing at random (MAR) missingness. When $\Delta \neq 0$, (8) will introduce a scenario of MNAR. A similar idea was also presented in the recent publication “*The Prevention and Treatment of Missing Data in Clinical Trials*” by the National Academy Press. The selection of the plausible values for the shift parameter (Δ) is discussed in Section 3.

Note that per recommendation in Wang and Daniels (2011), only the observed data within the pattern is assumed to be multivariate normal. The observed data distribution can be expressed in terms of the marginal distribution of baseline measurements and the conditional distributions of postbaseline measurements given earlier measurements. Assuming that these distributions are normal, the linear regression of each observation on prior observations will yield least-squares estimates of model parameters that can be utilized for independent posterior draws of model parameters for observed data. The multiple imputation approach will be used to estimate the overall mean at the final time point.

2. Imputation Procedure

All the missing data will be imputed to create a complete dataset, then statistical analysis can be performed using appropriate techniques such as **MMRM**. The imputation **can accommodate** MNAR **missing data mechanisms**, based on the theory discussed in the above sections.

The model parameters for each dropout pattern, i.e., the mean, variance and proportions of observations in each pattern, are drawn from their posterior distributions prior to the imputation of missing data for a single imputation.

The details of imputation within a pattern, say Pattern t , are as the following:

Step 1. Impute the first missing value y_{t+1} for each patient in Pattern t ($t = 1, \dots, T-1$):

- a. Compute estimates of mixture probabilities $\lambda_{s-1,j}$ in (7) with $s = t+1$ given the posterior draw of proportions of observations in each pattern and the posterior draw of regression parameters for the observed data.

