- b. Draw a random integer from $\{s, \dots, T\}$ to index a component distribution on the right hand side of (6), using mixture probabilities obtained in a). Draw y_{t+1}^* from the identified component normal distribution. Impute the missing y_{t+1} as $\tilde{y}_{t+1} = y_{t+1}^* + \Delta$.

Step 2. Impute the rest of the missing values of $y_{t+2}, y_{t+3}, \dots, y_T$ for patients in Pattern t:

Starting with imputation for y_{t+2} , first, similar to Step 1, draw y_{t+2}^* from the normal mixture (6) based on the observed y_1, \dots, y_t and the already imputed \tilde{y}_{t+1} for the patient. Then the missing y_{t+2} is imputed as $\tilde{y}_{t+2} = y_{t+2}^* + \Delta$ with probability δ_{t+1} and as $\tilde{y}_{t+2} = y_{t+2}^*$ with probability $1 - \delta_{t+1}$, where the mixture probability $\delta_{t+1} = \omega_{t+1,t+1}$ is obtained from (4) given the posterior draw of proportions of observations in each pattern and the posterior draw of regression parameters for the observed data.

Missing values of y_{t+3} through y_T can be imputed similarly as y_{t+2} .

To summarize, the imputations of y_{t+1} through y_T is done recursively within each Pattern t (for all $t = 1, \dots, T - 1$) to create a complete dataset after imputation is done for all patterns with missing values.

The above imputation procedure is applied to all subjects in each missing data pattern to create a single imputed data set. Repeating the process of drawing parameters from the posterior distribution and imputing missing data given the posterior draw m times will yield m imputed data sets. The observed or imputed values at the final data point are averaged to obtain the overall mean estimate for each imputed data set, and the multiple imputation estimate is obtained by averaging the estimates across m imputations.

In this sensitivity analysis, m is set to equal to 20. The value of m is discussed in the context of imputation efficiency in standard multiple imputation theory (Rubin, 1987, p. 114), and $m = 20$ would provide at least 96% of relative efficiency as compared with using a large number of imputations (SAS/STAT User's Guide, p. 3796).

3. Determination of the Shift Parameter Values

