The common shift parameter Δ is the difference between the mean of y_{t+1} among those who drop out at Visit t and those who remain beyond Visit t ($1 \leq t \leq T - 1$). The exact value of Δ is unknown and can't be estimated from data because of missingness. The magnitude of Δ depends on the medical aspects of the trial. Using relevant historical data, one may select Δ as a proportion of the sample standard deviation or a proportion of observed treatment efficacy.

RESTRICTED

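### As visible, the missing-not-at-random check uses one shift with no treatment index, so it does not test rapastinel dropouts faring worse than placebo dropouts (minor, cheap to add)

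*SAP*

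**What the plan says.** SAP 8.1 offers a pattern-mixture analysis as its check on the missing-at-random assumption behind the primary MMRM. Patterns are defined by the last visit with an observed score, not by arm. The imputation assumes that "the distribution of the missing observations differs from the observed only by a shift parameter value", and the shift runs from 0 to 8 MADRS points, where higher is worse. Protocol 9.7.5.1 sets the same shift and says that the dataset "will be analyzed using the same model as the primary analysis for between-treatment group comparisons at the end of the treatment".

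SAP Appendix II gives the mechanics. Equation (8) moves the distribution of the first missing score by the shift. Steps 1 and 2 add it to the imputed values. Neither the equation nor the steps carry a treatment index, and "The above imputation procedure is applied to all subjects in each missing data pattern to create a single imputed data set". Section 3 of the appendix opens with "The common shift parameter" and defines it over dropout visits. It adds that the value may be chosen as "a proportion of the sample standard deviation or a proportion of observed treatment efficacy". On predictors, SAP 8.1 says only that "The observed MADRS total score at a visit is assumed to have a linear relationship with the patient's prior measurements".

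The sample-size section, SAP 12.0, assumed "a common drop-out rate of 10% during the randomized treatment period" for all groups, and it reports overall dropout below 5% at the blinded review. No visible text gives an arm-specific shift, a reference-based imputation or a tipping-point search by arm.

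**The concern.** The run exists to show whether the Day 21 result survives if dropouts fare worse than missing at random predicts. The case that threatens a finding for rapastinel is the asymmetric one, in which rapastinel dropouts lose more than placebo dropouts. Protocol 9.3.3 lists adverse events and lack of efficacy among the reasons for leaving, and Protocol 9.4.13 lets patients leave to start other treatment. These reasons need not act equally in the two arms.

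If both arms receive the same shift, equal dropout makes both arm means worse by the same amount and the difference hardly moves. Stability would then follow from the design and would be weak evidence of robustness. If placebo loses more patients, a larger shift moves the estimate towards rapastinel. At stake is how much reassurance the run gives when the primary result is close to the significance boundary.

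**Working it through.** **Inputs from SAP 12.0:** SD 8.7, correlation 0.5, 210 per arm, 2-sided 0.05, planned dropout 10% after randomization, observed overall dropout below 5%. **From SAP 8.1:** shift 0 to 8. **From SAP Table 14.1–2 and SAP 4.3:** six post-randomization visits (Days 8, 11, 14, 15, 18, 21), with at least one MADRS needed for the mITT population. That leaves five incomplete patterns.

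**The plan's own figures.** With 350 per arm, SD 10 and difference 3.25, SE = 10 × √(2/350) = 0.756. Power = Φ(3.25/0.756 − 1.96) = 99.0%, as stated. For the revised size, 2 × (1.96 + 1.2816)² × 8.7²/3.25² gives 151 per arm. Then 151/0.85 = 178 per arm, or 356 in total, against 360 stated. This carries 3.25 over, which is an assumption because the revised effect is not restated.

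**Ceiling.** If the whole shift survives to Day 21, the difference falls by shift × (rapastinel dropout − placebo dropout) under a common shift, and by shift × rapastinel dropout under a rapastinel-only shift.
- Common shift of 8: 0 at equal dropout; 8 × (0.05 − 0.03) = 0.16 at 5%/3%; −0.16, in rapastinel's favour, at 3%/5%.
- Rapastinel-only shift of 8: 8 × 0.05 = 0.40 at 5% and 8 × 0.10 = 0.80 at 10%.

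**What carries through the recursion.** Appendix II applies the shift in full only at the first missing visit. Under assumed compound symmetry with correlation 0.5, each of k prior scores has weight 1/(k+1). A shift of 8 then leaves about 8, 1.1, 1.3, 1.6 and 2.0 points at Day 21, from the latest dropouts to the earliest. With dropout spread evenly, the mean is 2.8, or 2.9 with the small later-visit term. So 5% rapastinel dropout gives 0.05 × 2.9 = 0.14.

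**Simulation of the procedure.** Settings: shift 8, 210 per arm, true effect 2.5, dropout completely at random, 20 imputations, arms pooled, prior scores as the only predictors. In Appendix II, "The model parameters for each dropout pattern, i.e., the mean, variance and proportions of observations in each pattern, are drawn from their posterior distributions". I skipped patterns too small to fit, which is my own rule. The analysis was a Day 21 ANCOVA on baseline, simpler than the SAP model. Mean loss in the difference, measured from the zero-shift run:

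| Dropout, rapastinel / placebo | Common shift | Rapastinel-only | Ceiling, rapastinel-only |
|---|---|---|---|
| 3% / 3% | about 0 | 0.09 | 0.24 |
| 5% / 5% | about 0 | 0.14 | 0.40 |
| 10% / 10% | about 0 | 0.31 | 0.80 |
| 6% / 4% | 0.07 | 0.18 | 0.48 |
| 7% / 3% | 0.12 | 0.21 | 0.56 |

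Fitting the regressions across patterns instead gave rapastinel-only losses of 0.135 to 0.142 at 5%/5% and 0.295 to 0.303 at 10%/10%, so the small-pattern rule does not drive the result.

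**Effect on the verdict.** SE = 8.7 × √(2/210) = 0.849, and the critical difference is 1.96 × 0.849 = 1.66. A loss of 0.14 matters only for observed differences of 1.66 to 1.80. The chance of landing there is 4.4% if the true difference is 2.5 and 1.3% if it is 3.25. With the 0.40 ceiling the chances are 14% and 5.0%. In the simulation, significance was lost at 5%/5% in 0% of trials with the common shift and 1.6% with the rapastinel-only shift. At 10%/10% the figures were 1.2% and 11.2%.

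**The case against.** The strongest objection is that nothing in the SAP says the shift is the same in both arms. The appendix ties the word common to visits, meaning one value across dropout times. Its notation carries no treatment index on anything, so the missing index on the shift proves little. The section on choosing the shift ends in general advice and never reaches the 0 to 8, so trial-specific text may be unseen. This stands as a caveat. Application to all subjects in each pattern makes the same shift in both arms the natural reading, but it remains an inference.

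Second, if the arms are pooled and treatment is not a predictor, the imputation already pulls rapastinel dropouts towards placebo. Leaving treatment out lowers the zero-shift estimate by 0.05 to 0.07 at 5% dropout and by 0.12 to 0.14 at 10%. The planned run may therefore test some loss of benefit, though by omission and at a fixed size that does not grow with the shift.

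Third, a reader might infer that the planned run must look stable at every shift. The documents do not support that, because dropout by arm is not given. With about 20 dropouts split by chance, an exact 10/10 split occurs only 18% of the time, and the SD of the between-arm difference is √20 = 4.5 patients, or about 2 percentage points. An imbalance such as 6%/4% is ordinary, and the common shift then does respond. It responds to the imbalance, however, and in either direction, not to rapastinel dropouts doing worse.

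Finally, the remark about scaling to observed efficacy is optional guidance. The operative values are fixed at 0 to 8, so I put no weight on it.

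**Conclusion.** The point holds as a minor gap. On the natural but inferred reading, the planned run does not examine rapastinel dropouts faring worse than placebo dropouts, which is part of what a check on missing at random should cover. At shift 8 the untested scenario costs about 0.14 points at 5% dropout per arm (ceiling 0.40) and about 0.31 at 10% (ceiling 0.80). If the below-5% overall figure includes lead-in losses, the 3% row (0.09) is nearer.

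These sizes rest on compound symmetry, even dropout timing, an illustrative true effect of 2.5, my rule for small patterns and a simplified analysis model. The verdict window also uses an unadjusted SE. Only a borderline Day 21 result would be affected.

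A reader might go further and infer that the primary analysis is biased or that the sensitivity analysis is worthless. Neither follows. The primary MMRM is untouched by this choice, and the common-shift run still shows what unequal dropout does.

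**What to change.** In SAP 8.1 and Appendix II, add a run in which the shift applies to rapastinel dropouts only and placebo dropouts stay at zero shift (missing at random). Run it from 0 to 8 and on to the tipping point. Going beyond 8 matters: at 5% dropout SE = 8.7 × √(2/199.5) = 0.871, so for an observed difference of 2.0 the tipping shift is (2.0 − 1.96 × 0.871)/0.05 = 5.9 if the full shift reaches Day 21. If only 2.9 of every 8 points carries through, it is about 5.9 × 8/2.9 = 16.

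Put treatment in the imputation regressions for this run, so that zero shift matches the primary MMRM assumption. Keep the common-shift run as a supplement, and say in one sentence that it is common to both arms, if that is the intent.

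The cost is a few sentences and slightly more programming, since the same code runs with the placebo shift set to zero. Sample size, primary analysis and alpha do not change. The downside is that the sensitivity result may look less favourable.

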8.2 KEY SECONDARY EFFICACY PARAMETERS

[figure not shown]
There are 3 key secondary efficacy parameters as listed below:

[figure not shown]
1. Change from baseline to Day 8 (1 Day after the first randomized treatment) in MADRS total score for mITT population
2. Change from baseline to Day 21 in MADRS total score for the placebo non-responders of mITT population
3. Change from baseline to Day 8 in MADRS total score for the placebo non-responders of mITT population

The key secondary parameters will be analyzed using the same MMRM model as for the primary efficacy parameter, except the placebo responder status at Day 7 will be excluded for the analyses of the 2nd and 3rd key secondary efficacy parameters listed above. A sequential testing procedure will be used to control the overall type I error rate at 5% for the comparisons of between-treatment difference of multiple secondary efficacy parameters in the order listed above. Specifically, the change from baseline to Day 8 in MADRS total score for the mITT population will be tested first at the significance level of 0.05. If the between-treatment comparison is statistically significant, then the analysis of 2nd and 3rd key efficacy parameters for the placebo non-responders will be performed at the same significance level sequentially as long as the treatment effect is statistically significant in the preceding testing.

Plots of fitted (least squares) mean values and their standard errors based on the MMRM model for the change in MADRS total score will be presented by treatment group and by visit.

9.1 ADVERSE EVENTS

AEs will be coded using the *Medical Dictionary for Regulatory Activities* and reported separated for placebo lead-in, randomized treatment, and safety follow-up periods.

[figure not shown]
An AE (classified by preferred term) will be considered a treatment-emergent adverse event (TEAE) if it was not present before the first dose of DB IP (i.e. the first IP during the placebo lead-in period) or was present before the date of the first dose of DB IP and increased in severity after the first dose of DB IP. An AE that becomes serious after the date of the first dose of DB IP will also be considered as TEAE. If more than 1 AE was reported before the first dose of DB IP and coded to the same preferred term, the AE with the greatest severity will be used for comparison with the AEs occurring during each study period analyzed. An AE that occurred more than 30 days after the date of the last dose of DB IP (including the randomized IP) will not be considered as a TEAE.

[figure not shown]
The number and percentage of patients reporting TEAEs and TEAEs leading to study discontinuation in each treatment group will be tabulated by system organ class and preferred term and further categorized by severity and causal relationship to the IP. If more than 1 AE is coded to the same preferred term for the same patient, the patient will be counted only once for that preferred term using the greatest severity and strictest causality for the summarization by severity and causal relationship.

[figure not shown]
The incidence of common ($\geq 2\%$ of patients in any treatment group) TEAEs will be summarized by preferred term and treatment group and sorted by decreasing frequency for the test treatment.

[figure not shown]
A serious adverse event (SAE) that occurred between the date of the first dose of DB IP and 30 days after the date of the last dose of DB IP, inclusive, will be considered a treatment-emergent SAE (TESAE). The number and percentage of patients who have TESAEs will be summarized by preferred term and treatment group.

[figure not shown]
Listings will be presented for patients with SAEs, patients with AEs leading to discontinuation, and patients who die (if any). All patients with SAEs, including SAEs reported during the screening period and the safety follow-up period, and patients discontinuing because of AEs occurring before the start of randomized IP will be included in these listings.

[figure not shown]

[figure not shown]

RESTRUCTURED

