**9.1.1****Screening Period**

After providing written consent, patients will enter a screening period of up to 14 days. The screening/washout period will be up to 2 weeks prior to Visit 2. Screening procedures may be conducted on up to 2 separate dates where necessary to accommodate patient and study center schedule; however, every effort should be made to conduct all procedures as early as possible in the screening period and the rater-administered MADRS and computer-administered MADRS must be collected on the same date. Patients will not receive any investigational product (IP) during the screening period but must continue their background ADT at the same dose. Patients meeting the eligibility criteria at the end of Visit 2 (Baseline) will be assigned a treatment by the interactive web response system (IWRS) and enter the double-blind treatment period.

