### 9.5.2.1 *Adverse Events*

An AE is any untoward medical occurrence in a patient or clinical investigation patient administered a pharmaceutical product and which does not necessarily have to have a causal relationship with this treatment. An AE can therefore be any unfavorable and unintended sign (including an abnormal laboratory finding, for example), symptom, or disease temporally associated with the use of a medicinal product, whether or not considered related to the medicinal product (ICH-E2A).

For the purpose of the study center's data collection responsibilities, any untoward event that was reported from the time the patient signed the ICF until 30 days after the final protocol-defined study visit or the last known dose of IP (if the final visit does not occur) is to be considered an AE.

Examples of AEs are as follows:

- Changes in the general condition of the patient
- Subjective symptoms offered by or elicited from the patient
- Objective signs observed by the Investigator or other study center personnel

- All diseases that occur after signing informed consent, including any change in severity or frequency of pre-existing disease
- All clinically relevant abnormalities in laboratory values or clinically relevant physical findings that occur during the study schedule

Please note that medical procedures scheduled prior to consenting, but occurring during the study should not be captured as AEs, but should be listed in the medical history if related to a pre-existing condition.

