### **9.7.6.1 *Adverse Events***

All AEs will be coded by system organ class and preferred term using the *Medical Dictionary for Regulatory Activities*.

An AE (classified by preferred term) will be considered a treatment-emergent adverse event (TEAE) if it was not present before the first dose of IP or was present before the date of the first dose of IP and increased in severity after the first dose of IP. **An AE that becomes serious after the date of first dose of IP will also be considered as a TEAE.** If more than 1 AE is reported before the first dose of IP and coded to the same preferred term, the AE with the greatest severity will be used for comparison with the AEs occurring during the double-blind treatment period that were also coded to that preferred term. An AE that occurs more than 30 days after the date of the last dose of IP will not be considered as a TEAE.

The number and percentage of patients reporting TEAEs in each treatment group will be tabulated by system organ class and preferred term and further categorized by severity and causal relationship to the IP. If more than 1 AE is coded to the same preferred term for the same patient, the patient will be counted only once for that preferred term using the greatest severity and strictest causality for the summarization by severity and causal relationship.

A **serious adverse event (SAE)** that occurred between the date of the first dose of IP and 30 days after the date of the last dose of IP, inclusive, will be considered **a treatment-emergent SAE (TESAE).** The number and percentage of patients who have TESAEs will be summarized by preferred term and treatment group. In addition, the incidence of TESAEs that **lead** to death will be summarized separately by preferred term for each treatment group.

*Overall summaries of AEs will be provided on a per-patient basis for categories of all TEAEs, treatment-related TEAEs, TESAEs, and TEAEs leading to study discontinuation.*

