2.0 INTRODUCTION

Study RAP-MD-03 is a Phase 3, multi-center, randomized, double-blind, placebo-controlled, parallel-group study in patients who are 18 to 65 years of age, meet DSM-5 (Diagnostic and Statistical Manual of Mental Disorders, Fifth Edition) criteria for Major Depressive Disorder (MDD), have a minimum score of 25 on the Montgomery-Åsberg Depression Rating Scale (MADRS), and have an ongoing inadequate response to antidepressant therapy (ADT).

[figure not shown]
The study will consist of up to a 14-day screening and washout period followed by a 1-week placebo lead-in period, a 2-week randomized treatment period, and then a 1 week of safety follow-up period. Both the placebo lead-in period and randomized treatment period will be conducted in a double-blind (DB) manner. Consequently, the combination of these two periods is referred to as the DB treatment period.

[figure not shown]
Signed informed consent from the patient or the patient's legally authorized representative will be obtained before any study-related procedures are begun. At the end of the screening period, patients meeting the eligibility criteria for this study will be enrolled into a 1-week, double-blind, placebo lead-in period intended to identify placebo responders. Placebo responders will be defined by meeting at least 1 of the following criteria at any time point during the 1-week double-blind placebo lead-in:

[figure not shown]
- Patients with \geq 50% decrease from Day 0 MADRS total score
- Patients achieving a MADRS total score of \leq 14 points

Upon completion of the placebo lead-in period, patients will be randomized in 1:1 ratio to receive either rapastinel 450 mg or placebo, adjunctive to ongoing ADT. Randomization will be stratified by patient's responder status (as placebo non-responder vs. placebo responder) achieved during the end of the placebo lead-in period. The schedule of visits and procedures for study RAP-MD-03 is presented in [Table 2-1](#). The study design is shown graphically in [Figure 2-1](#).

This SAP provides a more technical and detailed elaboration of the statistical analyses of efficacy and safety data as outlined and/or specified in the final study Protocol Amendment 2 (version dated 20NOV2018) and the Restricted Access Addendum Amendment 2 (version dated 20NOV2018). Specifications of tables, figures, and data listings are contained in a separate document.

RES1

[figure not shown]

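### The TEAE rule lets a resolved screening event suppress a non-serious new onset of the same preferred term after dosing

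*SAP*

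**What the plan says.** SAP section 9.1 classifies adverse events by preferred term. An event is treatment-emergent if the term was not present before the first dose of DB IP, or if it "was present before the date of the first dose of DB IP and increased in severity after the first dose of DB IP". An event that becomes serious after that dose also counts. A further sentence names the comparator where there are several candidates: "If more than 1 AE was reported before the first dose of DB IP and coded to the same preferred term", the most severe of them is set against the events in each study period. Protocol section 9.7.6.1 has the same structure; its second limb covers an event that "was present before the date of the first dose of IP and increased in severity after the first dose of IP".

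The pool of earlier events is set elsewhere. Protocol section 9.5.2.1 treats as an AE "any untoward event that was reported from the time the patient signed the ICF until 30 days after the final protocol-defined study visit", so screening events are recorded as AEs. Protocol section 9.1.1 gives the length of that window: "The screening/washout period will be up to 2 weeks prior to Visit 2". SAP section 2.0 places a further stage before randomized treatment: "The study will consist of up to a 14-day screening and washout period followed by a 1-week placebo lead-in period".

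Neither document requires the earlier event to be ongoing at the first dose, and neither says that a new episode after resolution counts.

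**The concern.** The usual purpose of a worsening limb is to avoid attributing to treatment a condition that was already there when treatment began. That purpose needs only events still ongoing at the first dose. As written, the rule also brings in events that had ended. Suppose a patient has a moderate headache that resolves in screening, and a separate mild or moderate headache after dosing. The second headache has a post-dose onset but is not a TEAE.

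Such events drop out of the TEAE summaries by system organ class, severity and causality, out of the table of TEAEs leading to discontinuation, and out of the common-TEAE table. The reported incidence of a term would then be too low.

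**Working it through.** The documents state no figure on this point, so there is none to reproduce. The check applies the written rule and then asks how much it could matter.

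**Step 1: classification.** Take a patient whose only earlier event of a term resolved before the first DB dose, and who then has a new event of that term. Under the written rule it is a TEAE only if it is more severe than the earlier one or is serious. For non-serious events:

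| Resolved screening event | New event mild | New event moderate | New event severe |
|---|---|---|---|
| Mild | not a TEAE | TEAE | TEAE |
| Moderate | not a TEAE | not a TEAE | TEAE |
| Severe | not a TEAE | not a TEAE | not a TEAE |

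Six of the 9 non-serious combinations are excluded, and none of the 9 serious ones. If only ongoing events served as comparators, all 18 would be TEAEs. These are counts of combinations, not of patients.

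**Step 2: the window.** It runs from consent to the first DB dose, at most 14 days. Under SAP section 2.0 that dose is the placebo lead-in dose, and randomized IP starts about 7 days later. Lead-in events therefore cannot mask anything. A masking event would have been reported roughly 7 to 21 days (7 + 14) before the first randomized dose.

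**Step 3: share of cases lost.** Let
- q = share of patients with a resolved screening event of the term;
- p = post-dose risk of the term in other patients;
- r = post-dose risk in those with the screening event;
- m = share of their recurrences that are non-serious and no more severe than the earlier event.

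Share lost = q·r·m / [(1 − q)·p + q·r].

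None of these four is in the documents. With equal risk (r = p) the expression reduces to q·m, which is at most q. For an assumed q of 3–8%, at most 3–8% of that term's cases are lost. If r exceeds p, the share rises. With p = 10%, r = 30% and m = 1:
- q = 5%: 0.015 / (0.095 + 0.015) = 13.6%;
- q = 8%: 0.024 / (0.092 + 0.024) = 20.7%.

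**Step 4: the comparison between arms.** Take 210 patients per arm (SAP section 12.0), assumed true incidences of 15% and 10% (31.5 and 21 cases), and the same share lost in each arm:

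| Share lost | Rapastinel | Placebo | Difference (points) | Cases lost | Ratio |
|---|---|---|---|---|---|
| 0% | 15.00% | 10.00% | 5.00 | none | 1.5 |
| 3% | 14.55% | 9.70% | 4.85 | 0.9 and 0.6 | 1.5 |
| 5% | 14.25% | 9.50% | 4.75 | 1.6 and 1.1 | 1.5 |
| 8% | 13.80% | 9.20% | 4.60 | 2.5 and 1.7 | 1.5 |

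**Step 5: the 2% table.** SAP section 9.1 tabulates terms reaching 2% in any arm. With 210 per arm, 2% is 4.2 patients: 5 patients (2.4%) qualify and 4 (1.9%) do not. One masked patient can remove a term at that edge if the other arm is also below 2%.

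**The case against.** The strongest reply is about wording. An event that was present before dosing and increased in severity afterwards can naturally describe a continuing condition that worsens, and the greatest-severity sentence addresses only the case of several same-term reports. That sentence nevertheless selects among events *reported* before the dose, with no condition on resolution, and nothing in either document supports the narrower reading. If the narrower reading is what the sponsor intends, the text still needs to say so, because a programmer following it literally would suppress these events.

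Other replies limit the point, and they stand:

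- Serious recurrences are not lost. They count as TEAEs, and treatment-emergent SAEs are defined by date alone.
- Masking depends on a condition fixed before randomization, so it should be similar in the two arms.
- Some safety outputs do not use the rule. Perceptual disturbance, increased suicidality and site reaction are tabulated by arm and visit (SAP section 7.1), and BPRS+ and CADSS have their own scores and visit windows (SAP sections 14.1 and 14.2). Discontinuations because of AEs are listed.
- SAP section 14.6 imputes only start dates, so a rule that depends on resolution needs a convention for missing stop dates.

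It can also be said that counting every post-dose onset labels recurrences of episodic symptoms as emergent. That is true, but they are counted in the concurrent placebo arm too, which shows the background rate.

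A reader might infer from the word washout that screening itself generates the masking symptoms. The documents do not support this: protocol sections 9.1.1 and 9.4.1 keep the background antidepressant at a constant dose, and the visible text does not say what is washed out. A reader might also picture the rule hiding a reaction to a first DB dose of rapastinel. Under the SAP, that first dose is placebo.

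**Conclusion.** The point holds for non-serious events. As written, a new onset after dosing is not a TEAE if a resolved screening event of the same preferred term was of equal or greater severity. Absolute TEAE rates are understated in both arms and the risk difference shrinks modestly. The ratio is roughly preserved provided the share masked is similar between arms, which randomization makes reasonable but does not guarantee: recurrences could differ by arm in frequency or severity.

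The size cannot be derived from the documents. It is probably small, given a window of at most 14 days, and largest for common recurring terms. With equal risk the loss is bounded by q. The losses of 13.6% and 20.7% in the working should not be read as estimates: they need a threefold higher risk in the affected patients and every recurrence to be no more severe than the earlier event, and the documents support neither. Nor do the documents support reading this as a bias that favours one arm, or as a loss of serious events.

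**What to change.** In SAP section 9.1, and to match in protocol section 9.7.6.1:

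1. Count as a TEAE any AE with onset on or after the first dose of DB IP, subject to the existing 30-day limit.
2. Count an AE ongoing at that dose only if it then worsens or becomes serious, and limit the same-term severity comparison to such ongoing AEs.
3. State how a missing stop date is handled, for example by treating an earlier AE as resolved only if a stop date before the first dose is recorded.

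The cost is a few sentences and a small programming change using AE start and stop dates that SAP section 14.6 already draws on. TEAE counts would rise slightly in both arms and would include some recurrences of pre-existing episodic symptoms. Design, conduct and data collection do not change.
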